19. QUALITY CONTROL AND QUALITY ASSURANCE PROCEDURES.....	23
20. ETHICS	24
20.1. Approvals.....	24
20.2. Participant Confidentiality	24
21. DATA HANDLING AND RECORD KEEPING	24
22. FINANCING AND INSURANCE	24
23. PUBLICATION POLICY.....	24
APPENDIX A: SCHEDULE OF PROCEDURES.....	25
APPENDIX B: C-Eye X TEST RESULTS TABLES	26
Appendix 1.....	27
Appendix 2.....	32

1. SYNOPSIS / Study outline

Study title	Evaluating the use of eye-tracking technology in the diagnosis of neurological patients, including patients with reduced consciousness
Justification of Tests	Currently, the diagnostics of consciousness disorders in people who suffer severe brain damage is based on standardised behavioural assessment. However, behavioural diagnostics often fails because of the severe cognitive, sensory and motor deficits associated with impaired consciousness, or because of the heterogeneous etiology and pathophysiology associated with the condition. Diagnosing consciousness disorders is based on traditional psychological and psychiatric tests, which require verbal contact with the patient. The use of the visual communication channel in assessing the state of consciousness and diagnosing cognitive function seems perfect for patients who are unable to communicate verbally and lack the motor skills to communicate their needs to medical personnel and their caregivers. Recently published studies conducted with patients with disorders of consciousness using the eye tracking device, C-Eye, as an alternative communication tool, indicate its diagnostic potential for people with this condition.
Type of clinical trial	Observational study of a medical device after CE authorisation.
Participants of Tests	Brain-damaged neurological patients with communication barriers, diagnosed as being in unresponsive wakefulness syndrome (UWS) or minimal consciousness state (MCS), for whom sight may be the only route of communication.
Expected number of Study participants	The number of observations to be analysed in Poland and Germany combined is: 90
Planned sample size	90 (2 x 45) , where 45 – sample size for each Test: (Test 1 (MCSD): Minimum Awareness Detection, Test 2 (CFA): Cognitive Function Assessment)
Follow-up duration	No further follow-up of patients is planned.
Planned Study period	Total duration: 11 months: May 2022 - March 2023 Phase 1: Preparation for the Study: 2 months: May - June 2022 Phase 2: Observation study: 7 months: July 2022 - January 2023 Phase 3: Closing the Study: 2 months: February - March 2023
Primary objective of the Study	Evaluation of C-Eye X system application in the neurological diagnostics of patients with reduced consciousness.

Secondary objective of the Study	Comparing the results of C-Eye diagnosis with those obtained from commonly used behavioural and psychological scales in the evaluation of patients with reduced consciousness.
Exploratory aim	Demonstrating that diagnostics of the state of consciousness and cognitive function of patients with consciousness disorders performed using C-Eye X allows a more objective assessment of the condition of patients who, according to traditional methods, remain in no contact with the surrounding world.
Primary endpoint	Obtaining reliable clinical data confirming the diagnosis of the state of consciousness and cognitive function of patients with reduced consciousness, in whom the diagnostic tool developed during the project was applied.
Secondary endpoint	Evaluation of differences between the results of the state of consciousness and cognitive functions of patients with reduced consciousness obtained by behavioural methods and using C-Eye X
Device name	C-Eye X
Manufacturer	AssisTech Sp. z o.o.
Main application	Eye tracking in the diagnostics of consciousness disorders and cognitive functions of people with reduced consciousness and communication barriers.
Duration of device use to date (years)	7 years

2. BACKGROUND AND RATIONALE

The diagnostics of consciousness disorders in people who suffered severe brain damage is based on standardised behavioural assessment. However, behavioural diagnostics often fails because of the severe cognitive and motor deficits associated with impaired consciousness, or because of the heterogeneous etiology and pathophysiology associated with the condition. The need for an accurate diagnosis and prognosis goes beyond the needs of the patients themselves, as their care is associated with a significant stress burden, mainly due to the high uncertainty of the prognosis. Currently, the diagnosis of consciousness disorders and cognitive functioning is based on traditional psychological and psychiatric tests that require verbal contact with the patient. The use of the visual communication channel in diagnosis of the state of consciousness and cognitive function seems perfect for patients who are unable to communicate verbally and lack the motor skills to communicate their needs to medical personnel and their caregivers.

Studies published in recent years using the C-Eye eye-tracking device as an alternative communication tool among patients with disorders of consciousness indicate its diagnostic potential in this condition. A definite advantage of using the C-Eye system in this context is that the patient with reduced consciousness makes the decision to cooperate on their own. C-Eye is further characterised by non-invasiveness, adaptation to the neurological patient with visual and cognitive deficits, and easy and intuitive operation by the examiner-diagnostician.

The project will be implemented in a group of patients who, as a result of various causes (e.g. trauma, stroke, hypoxia), have suffered brain damage resulting in a significantly reduced state of consciousness, unable to communicate other than by eye movement (visual channel). The project will use the C-Eye X device, which is the next generation of the previously used C-Eye PRO system.

Previous publications in this area indicate that, despite significant deficits in the level of consciousness or cognitive function, such patients are able to establish communication by sight, and their memory or linguistic functions remain at a high level, allowing conscious communication using their sight.

Participation in the project poses no risk to the patient. The tasks that will be performed are not taxing on their functioning, nor do they carry the risk of impairing their health.

3. OBJECTIVES

The aim of this Study is to perform a clinical evaluation of the authors' original battery of diagnostic tests in the C-Eye X system, addressed to patients who have suffered damage to the central nervous system (CNS) and communicate with the help of the organ of sight (a test to differentiate patients' state of consciousness and a test to assess the level of cognitive function in patients), as well as to evaluate the proposed diagnostic method (procedure) (including the type and scope of diagnostic tasks and how diagnostic observation is carried out using the C-Eye X system). The intention of the project's authors is to introduce a novel diagnostic solution that will help reduce misdiagnoses (currently believed to be up to 40% of errors) made for such patients, due to the inadequacy of current behavioural tools to work with patients after severe brain damage.

3.1.Primary Objective

Evaluation of the application of the C-Eye X system (proprietary diagnostic tests – MCSD and CFA and eye tracking technology) in the neurological diagnosis of patients with reduced consciousness.

3.2. Secondary Objectives

Comparing the results of C-Eye diagnosis with those obtained from commonly used behavioural and psychological scales in the evaluation of patients with reduced consciousness.

3.3.Exploratory objective

Demonstrating that diagnostics of the state of consciousness and cognitive function of patients with consciousness disorders performed using C-Eye X allows a more objective assessment of the condition of patients who, according to traditional methods, remain in no contact with the surrounding world.

4. STUDY DESIGN

The Study will be conducted as an open-label Study..

After meeting the inclusion criteria, the patient will begin participation, which will last up to 15 days (one test) or up to 30 days (two tests) per patient. Patients can be added at different stages of the project; there is no requirement that all patients start participating at one time. Depending on the patient's state of consciousness (as determined by the Test 1 diagnosis or based on a previous CRS-R diagnosis prior to inclusion in the Study), they will complete a test to assess state of

consciousness (MCSD group) and/or a test to assess state of cognitive function (CFA group), in the case of a diagnosis higher than UWS. The decision to include a patient in one group or the other will be made by the investigator. Assuming that (for various reasons, dependent or independent of the patient/facility/investigator) not every patient will participate in the entire project (due to dropping out), the results obtained in 90 observations (45 per test) will be included in the analysis. This means that it is permitted to replace a patient excluded from the Study (during the course of the Study) with another patient. The permissible number of patients so replaced may not be greater than 10% of the total expected number of observations (i.e. for both groups combined: MCSD and CFA). The final decision to replace a patient excluded from the Study with another patient is made by the Primary Investigator. At the same time, it is assumed that the dropout rate allowed in the Study is 10% (i.e., the minimum number of patients who will participate in the entire Study is 81, total for both groups: MCSD and CFA).

The number of visits per patient will depend on the test and will be (see Appendix A for a detailed visit):

- **7 visits** (first initial visit – screening, next five screening visits, the final - seventh one – Closing Visit) for Test 1 – Minimally Conscious State Detection Test (MCSD Test)
- **5 visits** (first initial visit – screening, next three screening visits, the last - fifth one – closing visit) for Test 2 – Cognitive Functions Assessment Test (CFA Test)

4.1.Primary and Secondary Endpoints

Primary endpoint: Obtaining reliable clinical data confirming the diagnosis of the state of consciousness and cognitive function of patients with reduced consciousness in whom the diagnostic tool developed during the project was applied.

4.2. Study Participants

4.2.1. Overall Description of Study Participants

Participants will include people recovering from severe brain injury who meet the project's inclusion criteria. Thus, they will be neurological patients after brain damage with communication barriers, diagnosed as being in unresponsive wakefulness syndrome (UWS) or minimal consciousness state (MCS), for whom sight is the only route of communication.

4.2.2. Inclusion Criteria of study participants

Criteria for patient inclusion in the Study:

1. Completed 18 years of age.
2. Consent of the legal guardian to participate in the Study and access to medical records.
3. Medical diagnosis indicating damage to the central nervous system.
4. Having and sharing a description of imaging tests (alternatively MR or CT) and (alternatively) ophthalmoscopy, ophthalmology, auditory tests.
5. Presentation of a list of medications used by the patient that may affect the results obtained in tests of cognitive function.

6. Acceptance by a physician (e.g. neurologist, neurosurgeon, internist) to participate in a clinical trial, taken after reviewing the Study protocol, including there is a need to take into account:
 - a. the ability to communicate only by sight (no verbal, sign or other communication),
 - b. the absence of dementia and aphasic disorders before the event that led to CNS damage and the patient's current condition,
 - c. preserved at least one functioning eyeball (possibility of cooperation with an eye tracker).

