4.2.3. Exclusion Criteria

Criteria for excluding a patient from the Study:

1. Visual defect (refractive defect) diagnosed before the incident, requiring work with glasses with lenses of more than ± 3 diopters.
2. Inclusion of drug treatment during the Study (observation), which can affect the patient's cognitive functioning (both in terms of cognitive enhancement and impairment/dementia).

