8. INFORMED CONSENT

Informed consent to participate in the Study must be given by either the patient or the person legally responsible for the Study participant. The participant and/or the person responsible for the Study participant will be informed about the title of the Study, its objectives and goals, the ethics committee's approval issued, the conduct of the Study, and the possibility of withdrawing from participation in the Study at any stage.

Other information regarding the project and participation in the Study will be provided upon patient request.

Protection of personal data is ensured in accordance with Article 13 (1) and (2) of the General Data Protection Regulation of 27 April, 2016. (Hereinafter referred to as GDPR (Polish: RODO)).

The Patient Informed Consent Form for participation in the Study is attached as Appendix 1 to this protocol.

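### The numbered inclusion criteria omit the UWS or MCS diagnosis that defines the study population, and item 6a, worded as an ability to communicate by sight, works against enrolling UWS patients

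*Protocol*

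**What the plan says.** The protocol describes the population in three places, with three different conditions on sight.

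- Synopsis (section 1), participants: UWS or MCS patients "for whom sight may be the only route of communication".
- Section 4.2.1: patients "diagnosed as being in unresponsive wakefulness syndrome (UWS) or minimal consciousness state (MCS), for whom sight is the only route of communication".
- Section 4.2.2, item 6a: "the ability to communicate only by sight (no verbal, sign or other communication". This is a sub-item of physician acceptance, introduced by "including there is a need to take into account".

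The only diagnosis in the numbered list is item 3: "Medical diagnosis indicating damage to the central nervous system". Item 2 asks for "Consent of the legal guardian to participate in the Study and access to medical records". Section 8 is wider: "Informed consent to participate in the Study must be given by either the patient or the person legally responsible for the Study participant". Section 4.2.3 has two exclusions. One begins "Visual defect (refractive defect) diagnosed before the incident"; the other concerns drug treatment started during the study that can affect cognition.

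Section 7 starts a patient's participation once the inclusion criteria are met. It has physicians in both countries follow one screening procedure, using an evaluation form that the sponsor provides. Under sections 5 and 7, a patient goes on to Test 2 (CFA) after a Test 1 (MCSD) result above UWS, or enters it directly on an earlier CRS-R diagnosis of at least MCS-.

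**The concern.** The list that decides entry does not carry the diagnosis that defines the population, and the gap runs in two directions. It can admit patients outside the population (conscious, gaze-only communicators), and through 6a it can discourage patients inside it (UWS).

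The secondary endpoint is the difference between C-Eye X and behavioural results. Section 4.1 says that discrepancies will be taken as a reason to change how such patients are diagnosed. If entry favours patients already known to answer by gaze, part of any advantage of C-Eye X over CRS-R and MOCA may come from who was let in. If few UWS patients enter, the study has little material to show that MCSD gives a UWS result when it should. Analysis after enrolment cannot supply the patients who were not recruited.

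**Working it through.** No arithmetic applies, and the protocol gives no figure to reproduce. The check takes two types of patient through the six inclusion criteria and two exclusions, then compares the outcome with the stated population and the rules for entering each test.

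**Patient A: adult with CNS damage who is truly in UWS**
1. Items 1 to 5 (age, guardian consent, CNS damage, imaging descriptions, medication list) can all be met.
2. Items 6b (no earlier dementia or aphasia) and 6c (a functioning eye) can be met.
3. Item 6a read literally is not met, because a patient in UWS has no demonstrated ability to communicate by any route.
4. Sections 1 and 4.2.1 nevertheless include UWS. Section 3 gives the MCSD test the task of differentiating states of consciousness. Sections 5 and 7 treat UWS as a possible Test 1 result, since only a result above UWS opens Test 2. Section 3.3 is aimed at patients whom traditional methods find to be out of contact.

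The literal list works against a patient whom the rest of the protocol wants.

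**Patient B: conscious adult with CNS damage who communicates only by gaze**
1. Items 1 and 3 to 5 can be met.
2. Item 2 needs a legal guardian, whom many such patients would not have. Section 8 accepts the patient's own consent, so this filter is partial.
3. Item 6a is met exactly; 6b and 6c can be met.
4. Neither exclusion applies on grounds of consciousness.
5. Direct entry to Test 2 requires at least MCS-, which is a floor without a ceiling.

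The list can admit a patient who falls outside the population of sections 1 and 4.2.1.

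**Wording.** The synopsis makes sight a possible only route, section 4.2.1 an actual one, and 6a an ability. Patient A satisfies the first but not, read literally, the other two. Section 4.2.1 also presents the diagnosis as following from the inclusion criteria, and the list does not contain it.

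**Direction of the effect.** Section 4.1 lists oromotor/verbal and communication subscales in CRS-R, and naming and verbal fluency in MOCA. C-Eye X is answered by gaze. Selecting on working gaze together with no other channel favours C-Eye X in a comparison of percentage scores. Some of this belongs to the intended population; the added part comes from requiring the gaze ability in advance. The protocol gives neither the expected UWS share nor any score distribution, so the added part cannot be sized.

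**The case against.** The strongest reply is that 6a is not a stand-alone test. It is one thing to weigh when a physician accepts a patient after reading the protocol, and section 4.2.1, just above the list, names UWS and MCS. The bracket in 6a and the rationale in section 2 fit a natural reading: no channel other than sight. The sponsor's evaluation form, which is not shown, may name the diagnosis, and section 7 promises one procedure for all sites. Most of this stands. The intended population is clear, the force of 6a is softer than that of a numbered criterion, and variation between sites is possible but not shown. What remains is that the operative list omits the diagnosis, and that section 4.2.1 does not settle the UWS question, since it also says sight is the route. A form should carry out the protocol's criteria, not repair them.

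A reader might infer that none of the 45 MCSD observations could come from UWS patients, so that everyone would pass to Test 2. The documents do not support this. UWS at entry is a behavioural label, and the protocol's premise is that such labels are often wrong (section 3 cites up to 40% of errors). A patient can carry the label and still be thought able to use gaze. Entry status is also not the MCSD result that opens Test 2.

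A reader might also infer that a planned analysis of agreement in the UWS class is lost. Section 17.1 describes no such analysis. It compares percentage scores and their increases, and adds Passing-Bablok regression and correlation.

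**Conclusion.** The point holds as a mismatch between the stated population and the operative criteria. The numbered list lacks the UWS or MCS diagnosis and any ceiling on consciousness, so a conscious gaze-only patient could qualify, with guardian consent a partial filter. Item 6a, read literally, works against UWS patients and favours those already able to use the index test's channel, which can tilt the C-Eye X comparison with CRS-R and MOCA.

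The size cannot be derived from the protocol. It depends on how physicians read 6a, on what the evaluation form says, and on how many conscious patients are put forward. The conclusion rests on two assumptions: that the numbered list governs entry, as section 7 states, and that the form does not already correct it.

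**What to change.** Three changes, made together:

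1. Reword 6a to require that the patient has no functional communication by speech, signs or any other channel, apart from possible use of gaze. Drop ability to communicate by sight as a condition, and leave fitness for the eye tracker to 6c.
2. Add a numbered inclusion criterion: a UWS or MCS diagnosis documented before inclusion. The study's own CRS-R cannot serve here, because Appendix A places eligibility at Screening and the first CRS-R at Visit 1.
3. Use the same wording in the synopsis and sections 4.2.1 and 4.2.2.

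The cost is an amendment and one line on the patient evaluation form. The need for a documented earlier diagnosis may exclude a few patients who lack one. At present the protocol mentions a prior CRS-R diagnosis only for patients who bypass Test 1, so sites should be asked whether records for Test 1 candidates usually contain one.

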4.2.3. Exclusion Criteria

Criteria for excluding a patient from the Study:

1. Visual defect (refractive defect) diagnosed before the incident, requiring work with glasses with lenses of more than ± 3 diopters.
2. Inclusion of drug treatment during the Study (observation), which can affect the patient's cognitive functioning (both in terms of cognitive enhancement and impairment/dementia).

5. COURSE OF STUDY

It will take 7 months to conduct the clinical evaluation; the assumed period of implementation of the Study is July 2022 - January 2023. The following work will be carried out:

- Recruitment of patients (acquisition of target group): 45 observations (in total from all the facilities included in the Study) for the diagnosis of state of consciousness – Test No. 1 (MCSD), and 45 observations (in total from all the facilities included in the Study) for the diagnosis of cognitive functions – Test No. 2 (CFA); The majority of the group among whom the recruitment will be carried out will include patients residing in facilities in Poland, about 15 –20% will be patients from facilities in Germany.
- Conducting studies in an established group of patients at independent facilities in Poland and Germany. A detailed description of the activities undertaken during each visit and their sequence is presented in Appendix A.
- Depending on the patient's state of consciousness, they will participate in Stage 1 and/or Stage 2. The Study will consist of:

Stage 1: performing MCSD Test (5 x within 14 days). After this series of testing is completed, a possible test will be conducted:

Stage 2: performing examination using the CFA Test (3 x in 14 days).

The execution of MCSD will be preceded by a CRS-R test, while the execution of CFA will be preceded by a CRS-R and a MOCA test. Stage 2 can be conducted after a diagnosis above UWS is obtained in Stage 1, or bypassing Stage 1 if said diagnosis was obtained earlier, prior to inclusion in the Study, based on the CRS-R test.

6. SITE SELECTION:

1. Settled situation with local NHF (applies to Polish facilities) and/or have the right to undertake clinical trials.
2. The presence and secondment for the purpose of this Study of at least two persons – therapists (one of the specialties: physiotherapist, speech therapist, psychologist, educator, occupational therapist), with at least one year of experience in working with C- Eye, ready to work with the patient using C-Eye in the framework of the ongoing Study (in case one of them is unable to perform the work). The names of the therapists selected to work with C-Eye X in the clinical trial (investigators) must be known at the stage of signing the tripartite agreement (Centre - Sponsor - CRO).
3. Investigator Certification:
 - the investigator has to obtain a Certificate of Training Completion for: ‘Working with C-Eye X within the framework of a clinical trial’, confirming the ability to operate and work with the C-Eye X system; training organised by the Sponsor (after prior arrangement of the date and other organisational matters between the facility and AssisTech Sp. z.o.o.);
 - having or obtaining a GCP Certificate by the investigator.
4. Hours of operation with C-Eye (ensuring the availability of the investigator) are 9:00 a.m. - 6:00 p.m., conducting the Study depending on the patient’s activity/reactivity status.
5. Declaration of inclusion in the Study (using C-Eye), according to the following guidelines:

- about 10 observations per Test, per facility in Poland,
- about 5 observations per Test, per facility in Germany,

whereby the determination of the details of cooperation, including financial issues, is carried out on the basis of the concluded tripartite agreement (Centre - Sponsor - CRO), defining the principles of cooperation.

6. The rules for the therapist (investigator) to work with the patient are governed by the facility's internal regulations, but if the patient feels safer in the presence of a family member, the family member may be present with the patient during the examination, under the rules set by the Contractor.

